## 7.4 Final Study Visit

Study Day 380 (Visit #39)

1. Perform basic history and physical exam, emphasizing examination of any acute complaints.
2. Obtain blood for anti-Na-GST-1 antibody assays.

## 7.5 Early Termination Visit

Every attempt will be made to retain subjects once they have been enrolled. However, if for safety reasons, withdrawal of consent, or loss to follow-up, a subject is deemed by the investigators and/or SMC to be not eligible to receive the study product as per protocol, he/she will discontinue vaccinations. Volunteers will be encouraged to continue attending scheduled study visits to be followed for safety. Study subjects who discontinue the vaccinations or study participation early will not be replaced. Withdrawal from the study for any reason will not impact the subject's medical care.

The following activities will be performed at the early termination visit for subjects who withdraw, or are withdrawn or terminated from the study:

- Obtain interim medical history by interview of subjects and note any changes since the previous visit.
- All concomitant medications will be recorded on the appropriate data collection form (if within 28 days of subject's last vaccination or during the CHHI phase of the study).
- Information regarding adverse events/Serious Adverse Events will be assessed and recorded on the appropriate data collection form.
- A targeted physical examination may be performed by a study clinician licensed to make medical diagnoses and listed on the Form FDA 1572 as the Principal Investigator or co-investigator, if indicated based on review of interim medical history.
- Approximately 10 mL of venous blood may be collected for safety labs and performed by the local clinical laboratory (if prior to Visit 15 and if not recently obtained per study schedule).
- Approximately 40 mL of venous blood may be collected for antibody and cellular assays (if prior to Visit 15 and if not recently obtained).

Subjects who have undergone CHHI and who insist upon terminating the study prematurely and prior to completion of Day 197 will be recommended to take albendazole for hookworm infection (400 mg orally for three consecutive days). Follow-up care will be offered regardless of study participation, if so desired by the subject.

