#### **5.3.4 Handling of Withdrawals**

The primary reason for withdrawal from the study will be recorded on the appropriate data collection form. Subjects will be encouraged to complete the Early Termination Visit. The Early Termination Visit procedures are listed in **Section 7.5**. Although subjects are free to withdraw at any time or may be withdrawn by the Principal Investigator or appropriate co-investigator at any time, subjects who receive at least one dose of study vaccine will be encouraged to remain in the study for follow-up safety assessments and collection of venous blood samples for immunogenicity testing and fecal samples for parasitological testing. Every attempt will be made to follow all adverse events, including solicited injection site and systemic reactions, serious adverse events, and new-onset chronic medical conditions ongoing at the time of early withdrawal to resolution.

Subjects who have received *N. americanus* challenge by CHMI who withdraw or are withdrawn before Day 280 post-CHHI and who have not been treated with albendazole for hookworm infection must receive early presumptive treatment for hookworm or else agree to continue be followed until Day 297 (Visit #37) post-CHHI. Subjects who elect to withdraw from the study will not be subjected to additional research portions of the study (research blood collections, fecal collections, etc.) although they will be strongly advised to continue with the safety portions (i.e., fecal testing for hookworm eggs, safety laboratory tests) of the study.

Although subjects are free to withdraw at any time or may be withdrawn by the Principal Investigator or appropriate co-investigator at any time, subjects will be encouraged to remain in this study for safety follow-up assessments (at a minimum, by telephone if not in person) continuing through approximately study Day 140 for subjects who do not receive CHHI, or study Day 189 (approximately 6 weeks post-CHHI) for subjects who receive CHHI. In the latter case, volunteers will be encouraged to remain in the study until Day 189 to ensure that treatment with albendazole is given after the point where the hookworms would have become adult worms, since the medication is not effective against the immature forms of the worm.

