3. Collect prior week's weekly GI symptom memory aid and give new weekly GI symptom memory aid.
4. Obtain fecal sample for parasitological testing.

Study Day 189 (Visit #21)

1. Perform basic history and physical exam, emphasizing examination of any acute complaints.
2. Record vital signs.
3. Obtain fecal sample for parasitological testing.
4. Collect prior week's weekly GI symptom memory aid and give new weekly GI symptom memory aid.
5. Obtain blood for hematology, antibody and cellular assays.

Study Day 196 (Visit #22) – Telephone Call

1. Review interim medical history emphasizing any acute signs or symptoms (including entries on the GI symptom memory aid).
2. Collect concomitant medication information.

Study Day 203 (Visit #23)

1. Perform basic history and physical exam, emphasizing examination of any acute complaints.
2. Record vital signs.
3. Obtain fecal sample for parasitological testing.
4. Collect prior week's weekly GI symptom memory aid and give new weekly GI symptom memory aid.
5. Obtain blood for hematology.

Study Day 210 (Visit #24) - Telephone Call

1. Review interim medical history emphasizing any acute signs or symptoms (including entries on the GI symptom memory aid).
2. Collect concomitant medication information.

Study Day 217 (Visit #25)

1. Perform basic history and physical exam, emphasizing examination of any acute complaints.
2. Record vital signs.
3. Obtain fecal sample for parasitological testing.
4. Collect prior weeks' GI symptom memory aids and give two new weekly GI symptom memory aids.
5. Obtain blood for hematology.

Study Day 224 (Visit #26) - Telephone Call

1. Review interim medical history emphasizing any acute signs or symptoms (including entries on the GI symptom memory aid).
2. Collect concomitant medication information.

Study Day 231 (Visit #27)

1. Perform basic history and physical exam, emphasizing examination of any acute complaints.
2. Record vital signs.
3. Obtain fecal sample for parasitological testing.
4. Collect prior weeks' GI symptom memory aids and give two new weekly GI symptom memory aids.

5. Obtain blood for hematology, antibody and cellular assays.

Study Day 238 (Visit #28) - Telephone Call

1. Review interim medical history emphasizing any acute signs or symptoms (including entries on the GI symptom memory aid).
2. Collect concomitant medication information.

Study Day 245 (Visit #29)

1. Perform basic history and physical exam, emphasizing examination of any acute complaints.

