## 7.7 Clearance of Infection

In order to confirm that treatment with albendazole results in cure of experimental hookworm infection, participants will be asked to provide fecal samples 1, 1½ and 2 weeks following treatment (Days 290, 294 and 297), which will be examined for the presence of eggs by microscopy. Three negative samples are required as confirmation of successful treatment. As treatment with even a single dose of albendazole is currently highly effective (20, 71), and as this study is being conducted in a hookworm non-endemic area, cure following a 3-dose course of treatment is expected for all subjects (72). Nevertheless, if eggs are detected in post-treatment fecal samples, the participant will be given a second course of albendazole, with the same procedure for confirmation of successful treatment.

In addition, treatment with albendazole will be offered to any study participant who wishes to withdraw from the study (whether due to the occurrence of adverse events or for personal reasons) prior to study Day 280. In such an instance, the participant will be strongly encouraged to provide post-treatment fecal samples to ensure cure of the infection. Fecal samples at 1 week, 2 weeks and 60 days following albendazole treatment will be requested for subjects who terminate the study early.

If a female becomes pregnant during the course of the study, provisions for treatment of hookworm infection will be offered (i.e., albendazole treatment after the first trimester of pregnancy).

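### Protocol 7.5 ties the albendazole recommendation for challenged early leavers to Day 197, a day that is no scheduled visit and agrees with no other section

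*Protocol*

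**What the plan says.** Four parts of the protocol deal with challenged subjects who leave before the scheduled cure.

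- **7.5 Early Termination Visit.** Challenged subjects "who insist upon terminating the study prematurely and prior to completion of Day 197 will be recommended to take albendazole for hookworm infection". Follow-up care is offered whether or not the subject stays in the study.
- **7.7 Clearance of Infection.** Here "treatment with albendazole will be offered to any study participant who wishes to withdraw from the study", for any reason, "prior to study Day 280. In such an instance, the participant will be strongly encouraged to provide post-treatment fecal samples".
- **5.3.4 Handling of Withdrawals.** Challenged, untreated subjects who "withdraw or are withdrawn before Day 280 post-CHHI" "must receive early presumptive treatment for hookworm or else agree to continue be followed until Day 297 (Visit #37) post-CHHI". The section also encourages subjects to stay until "study Day 189 (approximately 6 weeks post-CHHI) for subjects who receive CHHI", because the drug does not work on immature worms. For what to do at the visit it points elsewhere: "The Early Termination Visit procedures are listed in" Section 7.5.
- **9.3.6 Reporting of Pregnancy.** A pregnancy that begins after challenge and before study Day 280 leads to deferred treatment.

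In the schedule (7.3 and Appendix A), challenge is on study Day 140, albendazole is dispensed on study Day 280 (Visit #34, window ±3 days), the third test-of-cure sample is taken on study Day 297 (Visit #37), and the last visit is study Day 380 (Visit #39). The contact nearest to Day 197 is a telephone call, "Study Day 196 (Visit #22"). The footnote on fecal samples in the CHHI-phase schedule also uses study Day 280 as the cut-off for withdrawals.

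**The concern.** The volunteers are healthy people infected by the study, and making sure that leavers are cured is a basic duty of the design. Section 7.5 lists what is done when someone leaves, and 5.3.4 sends staff there. The day in that list should agree with the rest of the protocol, and it does not.

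The limit also sits badly with the protocol's own reasoning. Section 5.3.4 sets study Day 189 as the point by which worms should be adult and the drug should work. The 7.5 instruction lapses about a week later, so it is silent over most of the period in which treatment is expected to succeed. The labels in 5.3.4, which should settle the matter, are themselves misprinted. What is at stake is a staff member acting on the wrong day.

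**Working it through.** The check is day arithmetic. Days after challenge = study day − 140.

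**The plan's own figure.** The Protocol Summary places treatment 20 weeks after challenge: 140 + 20 × 7 = 280. This reproduces study Day 280, so 280 is a study day and not a count from challenge.

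**Three readings of Day 197 in 7.5, against Day 280**

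| Reading | Study day | Against Day 280 |
|---|---|---|
| Study day, as printed | 197 (57 days, 8.1 weeks after challenge) | 280 − 197 = 83 days short |
| Slip for 297 | 297 | 297 − 280 = 17 days past |
| Days after challenge | 140 + 197 = 337 | 337 − 280 = 57 days past |

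None gives Day 280. The second gives a real visit, the third test-of-cure sample, which is also the follow-up end point in 5.3.4. But 7.5 does not require that the subject be untreated, so on that reading it would also recommend albendazole to leavers on Days 281 to 297, most of whom would already have been dosed.

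**Days on which the 7.5 sentence is silent, as printed.** From Day 198 to the day before scheduled dosing: 279 − 198 + 1 = 82 days. Challenge to the day before dosing: 279 − 140 + 1 = 140 days. The share is 82/140 = 58.6%. It counts days outside one sentence. Over those same days 5.3.4 and 7.7 both apply, so the number of days with no treatment provision in the protocol as a whole is 0.

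**Labels in 5.3.4**

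- Day 280 counted from challenge would be 140 + 280 = study Day 420, which is 420 − 380 = 40 days after the last visit.
- Day 297 counted from challenge would be 140 + 297 = study Day 437, whereas Visit #37 is study Day 297 (157 days after challenge).
- Study Day 189 is 189 − 140 = 49 days, or 7.0 weeks, after challenge. Six weeks would be 140 + 42 = study Day 182. The exploratory outcome measures (3.2.3) list sampling at 5 and 7 weeks, which matches the assays on Days 175 and 189 in Appendix A.

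**Dosing window.** Visit #34 may fall on study Days 277 to 283. A rule that simply says before study Day 280 would miss a subject who leaves untreated on Days 280 to 283. This is why treatment status is a better key than any single day.

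**The case against.** The strongest reply is that leavers are already covered. Section 5.3.4 makes presumptive treatment, or follow-up to Visit #37, mandatory for untreated challenged leavers. It also carries a duty without any day limit to offer curative therapy and to treat challenged subjects who stop attending. Section 7.7 offers the drug up to study Day 280, and 14.6 covers discontinuation of the study. Section 7.5 does not forbid later treatment; it is silent after Day 197, so all the rules can be followed together. This stands. A reader might infer from 7.5 alone that leavers on Days 198 to 279 go untreated, or read 58.6% as the share of the infection period without protection. The documents do not support either inference.

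The label errors are also said to resolve themselves. Visit #37 fixes Day 297, 7.7 and 9.3.6 fix Day 280, and the explicit study day fixes Day 189. Read literally, the Day 280 tag errs towards treating more people, and only those not yet treated. This stands too, so these are incidental corrections.

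Finally, 197 may simply be a misprint for 297, a coherent day because 7.7 requires three negative samples ending then. That is plausible, but nothing in the documents says so. It would still leave 7.5 out of line with 7.7 and without a condition that the subject be untreated.

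**Conclusion.** The concern holds as an internal inconsistency that should be fixed. The day in 7.5 is wrong or unexplained on every reading tried, and it stands in the operative early-termination text for infected volunteers. The size is modest: 82 days on which one instruction is silent while two other sections still apply. The possible harm is limited to staff acting on 7.5 alone. The documents give no withdrawal rate, so the number of subjects affected cannot be estimated.

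This rests on reading Days 280 and 297 in 5.3.4 as study days, which the visit numbering and the 20-week treatment time both support. There is no effect on sample size, power, alpha or the primary analysis. Whether 197 was meant as 297 is for the sponsor to say.

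**What to change.** **In 7.5**, replace the Day 197 limit with a treatment-status rule. Any subject who has undergone challenge and leaves without having received the scheduled albendazole (Visit #34, study Day 280 ±3) is handled under 5.3.4: presumptive treatment, preferably not before about study Day 189, or follow-up through study Day 297 (Visit #37). Make this subject to the pregnancy deferral in 7.7 and 9.3.6 and to the donor sub-study exemption in 7.8. Add that a subject who leaves after treatment but before Day 297 is asked to complete the test-of-cure samples.

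**In 5.3.4**, key the rule to not yet having been treated with albendazole in the same way. Delete the post-CHHI tag after Day 280 and after Day 297 (Visit #37), and change six weeks to seven for study Day 189.

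**Sponsor query.** Ask whether 197 was a slip for 297. The status rule works whatever the answer.

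The cost is a short rewording in two sections, with no added scheduled visits, subjects or analyses. The test-of-cure samples are already in the schedule.

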## 7.6 Unscheduled Visit

Unscheduled visits may occur at any time during the study. Procedures conducted at these visits may include any of the procedures detailed in **Appendix A** as appropriate at the discretion of the investigator depending on the nature of the unscheduled visit. Any of the following activities may be performed:

- Review concomitant medications (if prior to 28 days after a study vaccination or between study Days 140 to 297).
- Review solicited adverse events (if prior to 28 days after a study vaccination or between study Days 140 to 280).
- Review serious adverse events and new-onset chronic medical conditions.
- Obtain medical history by interview of subjects and note any changes since the previous visit (if indicated).

- A targeted physical examination may be performed by a study clinician licensed to make medical diagnoses and listed on the Form FDA 1572 as the site principal investigator or sub-investigator, if indicated based on review of medical history.
- Examine study vaccination site (if within 14 days after a study vaccination).
- Approximately 10 mL of venous blood will be collected for safety labs and performed by the study clinical laboratory (if indicated).

## 7.7 Clearance of Infection

In order to confirm that treatment with albendazole results in cure of experimental hookworm infection, participants will be asked to provide fecal samples 1, 1½ and 2 weeks following treatment (Days 290, 294 and 297), which will be examined for the presence of eggs by microscopy. Three negative samples are required as confirmation of successful treatment. As treatment with even a single dose of albendazole is currently highly effective (20, 71), and as this study is being conducted in a hookworm non-endemic area, cure following a 3-dose course of treatment is expected for all subjects (72). Nevertheless, if eggs are detected in post-treatment fecal samples, the participant will be given a second course of albendazole, with the same procedure for confirmation of successful treatment.

In addition, treatment with albendazole will be offered to any study participant who wishes to withdraw from the study (whether due to the occurrence of adverse events or for personal reasons) prior to study Day 280. In such an instance, the participant will be strongly encouraged to provide post-treatment fecal samples to ensure cure of the infection. Fecal samples at 1 week, 2 weeks and 60 days following albendazole treatment will be requested for subjects who terminate the study early.

If a female becomes pregnant during the course of the study, provisions for treatment of hookworm infection will be offered (i.e., albendazole treatment after the first trimester of pregnancy).

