This phenomenon has been observed in some clinical studies with CpG ODNs involving use of CpG 7909 as an antineoplastic agent, in which study subjects have developed detectable antibody to double-stranded DNA. These antibodies have generally declined to baseline after cessation of CpG 7909, and have not been associated with other autoimmune phenomenon, and their possible clinical significance is unknown. Subjects in the study described in this protocol will be closely monitored for laboratory evidence (e.g., anti-double stranded DNA antibodies or rheumatoid factor) or clinical signs or symptoms of autoimmunity.

Female subjects will be cautioned of the unknown risk of the Na-GST-1/Alhydrogel® vaccine administered with or without AP 10-701 or CpG 10104, and of hookworm infection (and of the albendazole used to treat hookworm infection) to the fetus. A female of childbearing potential, unless surgically sterile (i.e., bilateral tubal ligation, bilateral oophorectomy, or complete hysterectomy), at least 2 years postmenopausal, practices abstinence, or has a vasectomized partner, must practice effective contraception (including oral, intra/transdermal, intravaginal, or implanted hormonal contraceptives; intrauterine device (IUD); double barrier methods [condom plus foam or spermicide, diaphragm plus foam or spermicide], or the Essure procedure) until documented clearance of hookworm infection following treatment with albendazole. Female subjects will be counseled by a study team member, or referred to the health provider of their choice, for evaluation and institution of an appropriate contraceptive method.

Female subjects will be cautioned of the theoretical risk of albendazole during pregnancy. Per the FDA's categorization of drug risks to a fetus, albendazole is Category C, indicating that animal reproduction studies have shown an adverse effect on the fetus. However, teratogenicity in humans has not been observed, and a study of over 800 women treated with albendazole during the second and third trimesters demonstrated no adverse effects (70). Use in the first trimester, however, is still not recommended, but potential benefits may warrant use of the drug in pregnant women despite potential risks. Albendazole has been shown to cause embryotoxicity and skeletal malformations in pregnant rats and rabbits. Female subjects will be counseled on the potential risks of albendazole use during pregnancy at each weekly visit.

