## **9.4 Type and Duration of Follow-up of Subjects after Adverse Events**

AEs will be recorded if they start from the time of the first study vaccination (Day 0) up to 28 days after each dose of study vaccine, and from time of CHHI up to study Day 297 (to include the albendazole treatment period). AEs limited to AESI's and new-onset chronic medical conditions will be followed through approximately 6 months after the larval application (Day 380, approximately 10 months after the final vaccination).

SAEs will be followed from the time of the first study vaccination (Day 0 [Visit 1]) through resolution even if this extends beyond the study-reporting period (approximately 10 months after the third study vaccination [Day 380, Visit 39]). Resolution of an AE/SAE is defined as the return to pretreatment status or stabilization of the condition with the expectation that it will remain chronic.

Follow-up procedures, evaluations, and outcomes will be recorded on the appropriate data collection form.

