## 14.6 Study Discontinuation

If the trial is discontinued, subjects who sign the informed consent form, and are randomized and vaccinated will continue to be followed for safety assessments. No further study vaccinations or CHHI will be administered.

In the event that the study is discontinued, all subjects who received CHHI and who have been and who have not been treated for hookworm will be offered albendazole (3 daily oral doses of 400 mg). The subjects will be asked to follow up weekly for 2 weeks to ensure clearance of infection (see **Section 7.7**).

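### Section 14.6 gives two follow-up occasions against the three-stool cure rule in Section 7.7, and the Day 297 recording cutoff does not cover a second albendazole course through its test of cure

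*Protocol*

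**What the plan says.** **Cure rule.** Protocol Section 7.7: "Three negative samples are required as confirmation of successful treatment". For subjects who complete the infection phase, "participants will be asked to provide fecal samples 1, 1½ and 2 weeks following treatment (Days 290, 294 and 297"). If eggs are found afterwards, the subject receives a second course and cure is confirmed by the same procedure.

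**Early leavers.** The same section sets a different timetable: "Fecal samples at 1 week, 2 weeks and 60 days following albendazole treatment will be requested for subjects who terminate the study early".

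**Discontinued study.** Section 14.6 offers albendazole to challenged subjects who have not been treated, then states: "The subjects will be asked to follow up weekly for 2 weeks to ensure clearance of infection". A cross-reference to Section 7.7 follows directly. No number of stools is given.

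**What depends on clearance.** Section 2.3.1.2 requires contraception "until documented clearance of hookworm infection following treatment with albendazole". Exclusion criterion 2 in Section 5.2 uses the same end point. Section 14.4 counts at least a further month from clearance.

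**Recording windows.** Section 9.4 records adverse events "from time of CHHI up to study Day 297 (to include the albendazole treatment period"). Section 9.1 (item 5) ends unsolicited non-serious events on the same day, and Section 6.6 does so for concomitant medications. Section 7.6 limits medication review at unscheduled visits to the same end date. SAP Section 4.1 repeats Day 297 in the unsolicited-event outcome.

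**The concern.** There are two linked gaps at the end of treatment.

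First, the cure rule counts samples, while the discontinuation section gives a frequency of follow-up that, taken literally, supplies fewer occasions than the rule needs. These are healthy volunteers infected on purpose, so showing that the infection has gone is a basic obligation. A woman's contraception period is also measured from that point. The section would be used only while the trial is being shut down, which is a poor time for site staff to be working out which timetable applies.

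Second, the adverse-event window is meant to take in the treatment period, but its end is a fixed study day chosen for a single course. The protocol itself provides for a second course. For a retreated subject the fixed day can fall before the treatment is over, and it always falls before the second test of cure is complete.

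**Working it through.** **1. The plan's own timetable.** The first dose is on Day 280 (Section 7.3, Visit 34), with three daily doses, so the last dose is nominally on Day 280 + 2 = 282. Days from last dose to stool:

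- 290 − 282 = 8, against a nominal 7
- 294 − 282 = 12, against a nominal 10.5
- 297 − 282 = 15, against a nominal 14

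The differences are 1, 1.5 and 1 day, inside the ±3-day windows in Appendix A. The stated Days 290, 294 and 297 reproduce.

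**2. Exit routes against the three-sample rule.**

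| Route | Section | Stated follow-up after treatment | Occasions |
|---|---|---|---|
| Completer | 7.7 | 1, 1½, 2 weeks | 3 |
| Early leaver | 7.7 | 1 week, 2 weeks, 60 days | 3 |
| Study discontinued | 14.6 | once a week for two weeks | 2 |

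The third route reaches three occasions only if the day of treatment is counted, and a stool from that day cannot test cure. Otherwise three samples require either that one contact yields two stools or that the cross-reference brings in an extra sample from 7.7. That extra sample would be at 1½ weeks under one timetable and at 60 days under the other. Section 14.6 does not say which.

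**3. Timing of a second course.** Let P be the day of the positive stool. Assume, as the most favourable case, that treatment starts the same day. The last dose is on P + 2. Section 7.3 places the three stools 10, 14 and 17 days after the first dose (290 − 280, 294 − 280, 297 − 280), so the second test of cure falls on P + 10, P + 14 and P + 17.

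| Positive stool (P) | Second course | Second test of cure | Third stool beyond Day 297 |
|---|---|---|---|
| Day 290 | Days 290–292 | Days 300, 304, 307 | 10 days |
| Day 294 | Days 294–296 | Days 304, 308, 311 | 14 days |
| Day 297 | Days 297–299 | Days 307, 311, 314 | 17 days |

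After a Day 290 or Day 294 positive handled at once, the doses fit before the cutoff. After a Day 297 positive, two of the three doses fall after it, and all three do if treatment starts a day later. The third stool is always after Day 297. Even with the Day 290 visit at its earliest (Day 287), two weeks counted from the first dose, and the last stool three days early, it falls on Day 287 + 14 − 3 = 298.

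**The case against.** **Section 14.6 can be read as compatible.** It sets how often subjects are seen and gives no stool count. It cites the section that holds the three-sample rule, and the completer samples all fall within about two weeks. This argument stands to an important extent. A reader might infer that no subject in a discontinued study could ever be declared cured, and the documents do not support that: three stools could be collected if the site follows 7.7. What the argument does not remove is the mismatch of schedules, since 7.7 offers two timetables and 14.6 states a third.

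**The early-leaver timetable is not a contradiction.** It is tempting to add it to the charge because its third stool comes about six weeks later than a completer's. But it does ask for three samples, so it meets the rule's count, and a separate timetable for a separate group is a choice open to the sponsor. That these stools are requested or encouraged rather than compulsory follows from the right to withdraw.

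**Much safety information is still captured after Day 297.** Serious events are followed to resolution. AESIs and new-onset chronic conditions are collected to Day 380 (Section 9.4). Section 9.3.1 follows adverse events already open until they resolve, and Visits 38 and 39 include a history and examination. This stands, so it would be wrong to say that harms of a second course go unrecorded altogether. The SAP's adverse-event definition (Section 5.7.5.1) also reaches to the last study procedure, but an analysis definition cannot supply events or medications that the protocol's collection window leaves out.

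**Few subjects are affected.** Section 7.7 expects cure in everyone after the first course, and 14.6 applies only if the trial stops with challenged subjects untreated. This is correct and limits the priority of the point.

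**Conclusion.** The point holds in a limited form. Sections 7.7 and 14.6 disagree on how clearance is documented when the study is discontinued: three samples are required and two occasions are stated, and neither 7.7 timetable matches the interval in 14.6. This is an inconsistency to be reconciled; it does not show that clearance is impossible to document. The two-occasion count assumes one stool per weekly contact.

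The Day 297 cutoff for non-serious adverse events and concomitant medications does not serve its stated purpose for a retreated subject. With same-day action on a positive stool, the second test of cure ends 10 to 17 days after the cutoff, and any delay before retreatment adds to that. The course itself runs past the cutoff only after a late positive stool or a delayed start.

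The documents give no sensitivity for a single stool examination and no expected failure rate, so no probability of missed residual infection is offered. The primary endpoint, sample size and planned comparisons are untouched. The point is worth correcting because it concerns the safety of deliberately infected volunteers and the end of a contraception requirement, and because it is cheap to correct.

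**What to change.** 1. Reconcile Section 14.6 with Section 7.7 so that the discontinuation route states how many post-treatment stools are collected and when, and so that the number meets the cure definition. The sponsor chooses the timetable; this review takes no position on which is right.
2. In Sections 9.1, 9.4 and 6.6, extend the recording of non-serious adverse events and concomitant medications, for retreated subjects, through the second course and its test of cure. Carry the change to the places that repeat the Day 297 limit, including Section 7.6 and the unsolicited-event outcome in the protocol and SAP Section 4.1.

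The cost is protocol wording with a matching SAP edit, at most one extra stool per subject in the discontinuation route, and roughly two to three weeks of additional recording in the few subjects, if any, who need a second course.
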